#### 5.5 Screen Failures

Participants who are consented to participate in the third trimester of pregnancy, may be withdrawn from the study protocol before, during, or following the cesarean surgery if events arise such as to preclude them from participating in the remainder of the study. These participants will be considered "Screening Failures". The following list is non-comprehensive, but represents the most likely scenarios:

- Vaginal or non-cesarean delivery
- Development of exclusion-based criteria prior to cesarean surgery (i.e., severe preeclampsia, preterm delivery, NICU assessment likely, etc.)
- Severe complications during labor and/or delivery whereby the PI and/or patient's surgeon recommend a change in therapeutic response.

Withdrawn participants will be replaced at a proportion of 1:1. Procedures are as follows:

- Study personnel and investigators will be notified.
- Written documentation of withdrawal and reason for withdrawal will be noted per IRB protocol.
- Study personnel, investigators, and pharmacy will be informed of the need for replacement of pharmaceuticals due to participant withdrawal.
- Subsequent data to be collected from the withdrawn participant will be restricted to the minimum amount necessary to continue to monitor safety, i.e., side effect diary including questions of sedation, LSD short form, dizziness, lightheadedness, bad dreams, nausea, vomiting, pruritus, hallucinations.

# 6 Study Drug

Ketalar (Ketamine) (C13H16ClNO, 2-(2-chlorophenyl)-2-(methylamino) cyclohexan-1-one) is a cyclohexanone derivative with known analgesic and anesthetic properties. It inhibits biogenic amine uptake, binds opioid receptors, and inhibits N-methyl D-aspartate (NMDA) receptors.

Ketamine will be used for post-cesarean delivery analgesia. Specifically, it will be evaluated for its role in pain reduction, opioid reduction, and improved pain outcomes. In the non-obstetric surgical population, modalities such as intravenous ketamine are well-recognized as effective adjuncts in opioid-reduction strategies for postoperative pain. Ketamine is used off-label as standard clinical care in perioperative pain management for patients with a history of complex pain such as people with chronic

pain (treated or untreated), a history of or current symptoms of depression and anxiety, current smokers, and women with opioid or substance use disorders.

Ketamine is an approved drug or biologic being evaluated for a new indication, population, route of administration, or dosage level not specified in the FDA approved labeling.

#### 6.1 Dose Selection

Safety and Efficacy: Preclinical studies, including studies on animals, and clinical studies, including studies on non-pregnant women, have been conducted and provide reassuring data on minimal potential risks to postpartum women. [45 CFR 46.204 (a)]. The selected reference list below demonstrates experience with this drug in dosing regimens matching or exceeding the currently proposed dosing, in both pregnant and postpartum people. The data support low risks to this population. In the dosing regimen that we describe which is "sub-anesthetic" (i.e.,  $\leq 0.2 \text{ mg/kg/hr}$ , lower than the anesthetic dosing regimens), we expect that the risks are sufficiently low to justify studying it in this fashion.

# 6.2 Study Drug Preparation and Dispensing

The study drug, ketamine, will be sourced by investigational (IDS) Pharmacy at UPMC Magee Women's Hospital. The infusions will be packaged and labeled for use in the clinical research study per pharmacy protocols and guidelines. Ketamine will be prepared by pharmacy with dosing instructions. There will be no blinding.

For on-site preparation and dispensing of the study drugs, the following procedures will be followed. The pharmacist of record will: maintain adequate records confirming receipt, expiration dates, or other disposition information on the investigational drug; they will record the name of the individual to whom the drug is shipped, date, quantity, and batch number. They will secure the drug in a locked storage area and monitor to ensure proper storage conditions; they will also complete regular inventory to assure accurate indication of stock on hand, as well as proper recording of stock received, dispensed, and returned. For the patients enrolled for open label pharmacokinetic studies, the pharmacist will generate a label prior to dispensing the study drug, including the date dispensed, quantity and expiration information, drug strength and dose; they will affix the label to the dispensed drug. For dispensing and drug disposition recording, they will record the date dispensed, patient initials or other identifiers, drug treatments, quantity dispensed, initials of dispenser, date and amount of patient returns documented in study records (i.e., returned drug that cannot be re-dispensed). Filing and all drug documentation will occur within study records, medical records, and logs.

Following the cesarean delivery, the initial drug administration (via IV infusion) will begin 15 minutes (± 30 minutes) after cord clamping and declaration of clinical/ hemodynamic stability by the case anesthesiologist after delivery. The maintenance dose will start 60 min (range: +15min) after the initial loading dose. The infusion will be completely stopped 12 hours after the start of infusion. The same infusion pump will follow the patient throughout the postoperative period for 12 hours until completion of the study drug. No manipulation of the infusion pump will occur by the patient. Adjustments to the rate will be at the discretion of the study team and can be physically made by study personnel qualified and trained in these procedures, or by clinical care providers under direct orders from the study team.

#### 6.3 Dose Delays and Modifications

All subjects will be monitored for adverse events throughout participation in this trial. Events requiring a dose delay or adjustment are described below.

#### Adverse Event, Dose Delays or Adjustments Procedures.

Contingency for lowest dose not tolerated. Our preliminary data suggests that only 1/8 (12.5%) of individuals received an infusion rate lower than 0.05mg/kg/hr due to side effects. However, these data are not representative of our study population, so it is conceivable that PK or PD for side effects may differ in the immediate postpartum setting, and that the lowest loading dose may not be tolerated. If loading dose of 0.05mg/kg/hr is not tolerated, we will follow the dose adjustments in Table 1 and Figure 3 below.

# Events that Trigger Dose Adjustment Procedures:

- Persisting unresolved hemodynamic side effects defined as Systolic blood pressure <80 or >160,
   Heart rate <40 or >120^33
  - o Unresolved after 3 consecutive measurements within a 15-minute interval
- Persisting (i.e., unresolved within 1 hour of onset) side effects sedation, dizziness, lightheadedness, persistent itchiness, bad dreams, hallucinations, or other side effects that are reported as not acceptable to patients or clinicians, despite minimizing infusion rate.
- Table 1 includes procedures for dose adjustments.

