# 3.4 Endpoints

# 3.4.1 Primary Endpoint

Maximum Tolerated Dose (MTD). The MTD will be defined as the dose at which fewer than 33% of patients experience a DLT defined by intolerability.

Tolerability (dichotomous Yes/No)

Tolerability (YES) will be defined as: lack of adverse events (adverse event defined as: severe unresolved hemodynamic effect: systolic blood pressure <80 or >160, heart rate <40 or >120).

Lack of Tolerability will be defined as presence of any adverse event (i.e., severe unresolved hemodynamic effect: systolic blood pressure <80 or >160, heart rate <40 or >120).

A **DLT** event is defined by complete infusion cessation due to intolerable side effect acceptability ratings by patient, OR the experience of an intolerable event as defined above. The escalation of dosing will be as noted in Figure 2 and is based on a modified Fibonacci sequence  $^{101,102}$  with smaller proportional increases in dose in the escalation scheme. Escalations occur until 2 in a cohort of 3 to 6 experiences DLT (i.e., until  $\geq$ 33% of patients experience DLT at that dose). The dose **below** this level estimates the MTD.

Participants will be classified as having had a DLT if any of the following conditions are met:

- Persisting (i.e., unresolved after 3 consecutive measurements within a 15-minute interval)
  hemodynamic side effects defined as below and despite treatments or minimizing
  infusion rates as specified.
  - Systolic blood pressure <80 or >160
  - Heart rate <40 or >120
- Complete infusion cessation due to intolerable side effect acceptability ratings by patient

Primary Outcomes will be measured at a minimum of every 4-hours from the start of the ketamine infusion (t = 0) for 24-hours (12-hours post infusion cessation). Additional assessments will be administered between the 4-hour measurements if any adverse event or side effect is noted by the patient.

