If RASS -2 or below, OR Respiratory Rate is < 8	Hold infusion for 10 minutes - symptom recheck every 10 min until resolution	If no resolution within 1 hour:  D/C infusion based on investigator discretion and monitor subject for safety as described in Section 7.4 and 7.5	↓ dose by 50% (e.g., 0.05mg/kg/hr reduced to 0.025 mg/kg/hr) and continue infusion.	If no resolution within 1 hour:  D/C infusion based on investigator discretion and monitor subject for safety as described in Section 7.4 and 7.5	↓ dose by 50% (e.g., 0.025mg/kg/hr reduced to 0.013 mg/kg/hr) and continue infusion.	D/C infusion and monitor subject for safety as described in Section 7.4 and 7.5 Event qualifies as DLT
Dizziness, lightheadedness, bad dreams, persistent itchiness, hallucinations, nausea, vomiting, or other side effects rated by patient as Not Acceptable	Hold infusion for 10 minutes - symptom recheck every 10 min until resolution Supportive care medications in 9.1	If no resolution within 1 hour:  D/C infusion based on investigator discretion and monitor subject for safety as described in Section 7.4 and 7.5	↓ dose by 50% (e.g., 0.05mg/kg/hr reduced to 0.025 mg/kg/hr) and continue infusion.	If no resolution within 1 hour:  D/C infusion based on investigator discretion and monitor subject for safety as described in Section 7.4 and 7.5	↓ dose by 50%     (e.g.,     0.025mg/kg/hr     reduced to 0.013     mg/kg/hr) and     continue     infusion.	D/C infusion and monitor subject for safety as described in Section 7.4 and 7.5 Event qualifies as DLT
Nausea or Vomiting	Rescue medications as indicated in 6.6  Re-evaluate for symptom resolution 10 min after rescue medication  Hold infusion for 10 minutes - symptom recheck every 10 min until resolution	If no resolution within 1 hour:  D/C infusion based on investigator discretion and monitor subject for safety as described in Section 7.4 and 7.5	dose by 50%  (e.g., 0.05mg/kg/hr  reduced to 0.025  mg/kg/hr) and  continue  infusion.	If no resolution within 1 hour:  D/C infusion based on investigator discretion and monitor subject for safety as described in Section 7.4 and 7.5	dose by 50%  (e.g., 0.025mg/kg/hr  reduced to 0.013  mg/kg/hr) and  continue  infusion.	D/C infusion and monitor subject for safety as described in Section 7.4 and 7.5 Event qualifies as DLT

Figure 3. Dose adjustments based on patient-reported acceptability

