### 7.4 Safety Assessments/Procedures During Treatment

Maternal monitoring during the infusion will follow our clinical standards perioperative ketamine monitoring and the standard Magee system safety precautions for administration of a controlled substance will be in place to protect from any misuse. A licensed and qualified anesthesia provider (resident, fellow, nurse anesthetists, or anesthesiologist) will be present during the first 30 minutes of the infusion and will have the option to treat blood pressures >180/100 mm Hg or heart rate >110 bpm. The study infusion will be discontinued if 3 consecutive measurements within a 15-minute interval remain above protocol-defined limits despite intervention (section 6.3). Maternal side effect symptomology monitoring will occur throughout the ketamine infusion. Automated alerts for maternal side effect responses go to clinical and research staff for immediate action. Any report of side effects will trigger a blood draw for analysis and correlation to measured plasma levels.

An independent DSMB will define frequency of monitoring of tolerability and DLT data. The severity of adverse events are classified in section 10.1

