#### 8 Potential Risks and Benefits

# 8.1 Reasonably Foreseeable Risks Related to Study Drug

Common side effects of ketamine are sedation, dizziness, lightheadedness, bad dreams, hallucinations, euphoria, dysphoria, nausea, vomiting. These risks are minimized by using doses below the doses that we typically see these side effects. Seriousness: mild to moderate.

Uncommon effects of ketamine include hypertension or hypotension, tachycardia, or bradycardia. These risks are minimized as much as possible by using doses below the doses that we typically see these effects. If these effects are noted, the drug will be stopped until the effects dissipate. Should the effects not dissipate, the PI will evaluate and determine whether the patient requires additional care. If these uncommon effects are experienced, an SAE log will be completed and the IDSMB and IRB notified. Seriousness: mild to moderate

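### Three out-of-limit readings in 15 minutes both start dose adjustment (6.3, 9.1) and, after intervention, end treatment and define a DLT (7.4, 3.4.1); no text says whether the window restarts

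*Combined protocol and SAP*

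**What the plan says.** **Hemodynamic effects.** The limits are the same in Sections 3.4.1, 6.3 and 9.1: systolic pressure below 80 or above 160, heart rate below 40 or above 120. Four places attach a consequence to three consecutive readings in 15 minutes.

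- Section 6.3, list of triggering events: the adjustment procedures apply when the effect is "Unresolved after 3 consecutive measurements within a 15-minute interval". No prior treatment is required.
- Section 9.1: the same count defines the event for which supportive drugs may be given.
- Section 7.4: "The study infusion will be discontinued if 3 consecutive measurements within a 15-minute interval remain above protocol-defined limits despite intervention", with a cross-reference to Section 6.3.
- Section 3.4.1, DLT bullet: the same count defines persistence, for "hemodynamic side effects defined as below and despite treatments or minimizing" of the infusion rate.

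Section 3.4.1 also has a second route to a DLT. It is the occurrence of an intolerable event under the tolerability definition, which names a severe unresolved hemodynamic effect but gives no time window and no treatment condition.

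Table 1 in Section 6.3 has a hemodynamic row whose legible event cell lists only the limits. It goes on to drug treatment with 5 minutes of monitoring, then to 5-minute holds with rate halving on resolution. It makes discontinuation discretionary at an intermediate step, and it ends in discontinuation and a DLT.

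**Patient-rated effects.** The 6.3 list requires "Persisting (i.e., unresolved within 1 hour of onset) side effects sedation, dizziness" and other effects to be unacceptable despite a minimized infusion rate. The paragraph on patient-reported effects in the same section sends any effect rated unacceptable to Table 1, where the first action is "Hold infusion for 10 minutes - symptom recheck every 10 min until resolution".

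**The concern.** A threshold that opens a management sequence in one section and closes it in another has to be tied to a clock. Here the link is the requirement of prior intervention in 7.4 and 3.4.1, but the documents do not say when the count begins relative to that intervention. Staff following the 6.3 list, Table 1 or 7.4 could manage the same patient differently, and staff applying the two DLT wordings in 3.4.1 could classify her differently.

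DLT status is the only input to the escalation decision, and that decision produces the primary endpoint, the maximum tolerated dose (MTD). With 6 to 12 patients planned, a single classification can move the result by a dose level.

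**Working it through.** No figure in the plan depends on this point, so the check sets the texts side by side and then sizes one reclassification.

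**Step 1. Role of the three-in-15-minute count**

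| Place | Consequence | Prior intervention required? | Direction |
|---|---|---|---|
| 6.3 list | Adjustment begins | No | High and low |
| 9.1 | Supportive drugs may be given | No | High and low |
| 7.4 | Discontinuation, mandatory | Yes | High only |
| 3.4.1 bullet | DLT | Yes | High and low |
| 3.4.1 second wording | DLT | No, and no count or window | High and low |
| Table 1, hemodynamic row | Treatment first; discontinuation and DLT at the end | Count not in the legible event cell | High and low |

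**Step 2. Patient not treated inside the window.** At the third reading 6.3 and 9.1 apply. Section 7.4 and the 3.4.1 bullet are not met, because there has been no intervention. These rules do not collide. Only the second wording in 3.4.1 could already count her.

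**Step 3. Patient treated at the first high reading, as Table 1 appears to direct, and still high at the third.**
- 6.3 list: the adjustment trigger has just been met. Under Table 1 she can continue at a reduced rate if the effect resolves.
- 7.4: readings have stayed high despite intervention, so the infusion is discontinued.
- 3.4.1 bullet: the effect has persisted despite treatment, so she is a DLT.

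A new window starting at the intervention would separate these outcomes, but no section says that one starts.

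**Step 4. Patient with low values.** Sections 6.3 and 3.4.1 apply, but the discontinuation sentence in 7.4 does not cover her.

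**Step 5. Patient-rated effect.** Under the 6.3 list, adjustment waits for one hour without resolution and presupposes that the rate has already been minimized, so the condition for adjusting the rate assumes a prior adjustment. Under the next paragraph and Table 1, an unacceptable rating leads straight to a hold.

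**Step 6. Effect of one reclassification.** Section 3.4.1 stops escalation at 2 DLTs in a cohort of 3 to 6. The rest of the rule is taken as the conventional 3+3 (Figure 2 is not shown): 0/3 escalate, 1/3 expand, 1/6 escalate.
- 0/3 to 1/3: escalate becomes expand.
- 1/3 to 2/3: expand becomes stop.
- 1/6 (16.7%) to 2/6 (33.3%): escalate becomes stop.

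**Step 7. Illustration with assumed rates.** Let p be the chance that a patient is counted as a DLT. Then P(escalate) = (1 − p)³ + 3p(1 − p)² × (1 − p)³.

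Assume that 10%, 20% or 30% of patients reach the three-reading point after treatment, and that there is no other source of DLTs. None of these rates is in the documents.

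| Reach the point | All counted | Half resolve and are not counted | Difference |
|---|---|---|---|
| 10% | p = 0.10: 0.906 | p = 0.05: 0.973 | 0.07 |
| 20% | p = 0.20: 0.709 | p = 0.10: 0.906 | 0.20 |
| 30% | p = 0.30: 0.494 | p = 0.15: 0.814 | 0.32 |

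For p = 0.20: 0.512 + 0.384 × 0.512 = 0.709.

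**The case against.** The best defense is that the plan describes a sequence: persistence triggers adjustment and supportive drugs, and only persistence after those measures leads to discontinuation and a DLT. The qualifiers in 7.4 and in the 3.4.1 bullet support this, and 7.4 refers back to 6.3. That much stands, and it removes the conflict for the patient in Step 2. It does not settle Step 3, because a sequence needs a second window that the text never states, and because Table 1 appears to put treatment before the first window closes.

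Four stronger readings are tempting, and the documents do not support them.

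- A reader might infer that adjustment begins and treatment ends at one and the same moment for every patient. The intervention qualifiers rule that out.
- A reader might add the 5-minute steps in Table 1 and conclude that discontinuation falls at 15 minutes on one reading and at 30 on another. The row is partly illegible and the minutes figure in its final column is lost, so that contrast cannot be established.
- A reader might treat Section 8.1 as a further clock, because it says the drug is stopped when effects are noted. That section is a risk summary, and the pause it describes is temporary, which is compatible with the holds in Table 1.
- A reader might conclude that no patient-rated effect arising in the 60-minute load can lead to adjustment during the load. That follows only if the 6.3 list is read alone. The next paragraph and Table 1 supply a rule that acts on the rating.

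It is also fair to say that any ambiguity in a DLT definition moves 3+3 cohorts in this way, and that the documents give no frequency for this one.

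**Conclusion.** The inconsistency is real but bounded. The hemodynamic rules conflict for a patient already treated within the window who is still above limits at the third reading. Under the second DLT wording in 3.4.1, a patient who is adjusted and continues could also be counted. Low values are missing from the discontinuation sentence in 7.4. Discontinuation is mandatory in 7.4 and discretionary at an intermediate step of Table 1. The two patient-rated triggers within 6.3 disagree.

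Each affected patient can change a cohort decision, and with it the MTD. Under the assumed rates, the chance of escalating at one dose level shifts by 0.07 to 0.32. That range is illustrative: it assumes that every patient reaching the point is in the disputed group and that half of them resolve. The conflict among 6.3, 9.1, 7.4 and 3.4.1 does not depend on the illegible part of Table 1; the statement about where Table 1 begins does rest on its legible event cell.

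This should be corrected before further cohort decisions are made, because it governs both discontinuation and the primary endpoint. No view is taken on which clinical rule is right.

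**What to change.** Reconcile Sections 3.4.1, 6.3 (trigger list and Table 1), 7.4 and 9.1 so that three things are stated once and in identical words wherever they recur: when adjustment starts, when the infusion is discontinued, and when a DLT is counted. The reconciled text should make explicit:

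- whether the 15-minute measurement window restarts after an intervention;
- whether the second DLT wording in 3.4.1 carries the same persistence and treatment conditions as the bullet;
- whether the discontinuation rule covers low as well as high values;
- how the mandatory wording in 7.4 relates to the discretionary step in Table 1;
- which of the two patient-rated triggers in 6.3 applies.

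The sponsor and DSMB decide the clinical content and timing. The cost is one protocol amendment to wording, with no added procedures. If patients have already been treated, their DLT classifications should be checked against the reconciled text and any change reported to the DSMB.

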# 1 Protocol Overview

Study Description	The purpose of this study is to identify a tolerable dose for postpartum ketamine infusion using a maximum tolerated dose (MTD) 3+3 design. A loading dose over 1 hour will be the MTD variable to be tested, as our data suggest that ketamine side effects occur with the loading dose.
Study Population:	Patients having cesarean delivery (CD) who are either: 1) planning not to breastfeed; or 2) are receiving ketamine as part of clinical care, will be enrolled. Ketamine will be started in postpartum patients, after cord clamping.
Planned Sample Size:	The projected sample size will be a maximum of 12 patients with complete primary outcome data within the MTD 3+3 design.
Participating Institutions (if a multicenter clinical trial)	N/A

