# Patient Reported Side Effects Dose Delays or Adjustments

[figure not shown]
- Side Effect Acceptability ratings are defined in section 3.4.2. Patient reported side effects (i.e., dizziness, lightheadedness, bad dreams, nausea, vomiting, itchiness, and hallucinations: all are dichotomous outcomes). These side effects will be evaluated based on patient-specific reports of how "acceptable" or "unacceptable." Patients reporting side effects and rating them as "unacceptable" will follow the dose delay or adjustment described in the Table 1. If side effects are rated "acceptable" then no dose delays or adjustments will occur.
- Figure 3 Decision Chart for Acceptability Based dose revisions.

Table 1. Loading and Maintenance Dose Adjustment Procedures:

Systolic blood pressure <80 or >160, Heart rate <40 or >120  Monitor for 5 minutes minutes for symptom resolution  Monitor for 5 minutes for symptom resolution  If event does not resolve  Hold infusion for 5 box (e.g., 0.05mg/kg/hr) and continue infusion.  If event does not resolve  Hold infusion for 5 box (e.g., 0.05mg/kg/hr) and continue infusion.  May D/C infusion and monitor subject for safety as	Event	1st Action	2 nd 1	Action	3rd /	Action	If event does not resolve
Pressure <80 or >160,   Heart rate <40 or >120   Heart rate <40 or >1							
monitor subject for safety as described in Section 7.4 and described in Section 7.4 and 7.5  Event qualifies as DLT	pressure <80 or >160,	labetalol or hydralazine per managing anesthesiologist Monitor for 5 minutes for symptom	for 5 minutes - symptom recheck at 5	(e.g., 0.05mg/kg/hr reduced to 0.025 mg/kg/hr) and continue	for 5 minutes - symptom recheck at 5 minutes:  May D/C infusion based on investigator discretion and monitor subject for safety as described in Section 7.4 and	(e.g., 0.025mg/kg/hr reduced to 0.013 mg/kg/hr) and continue	minutes of unresolved hemodynamic effect:  D/C infusion and monitor subject for safety as described in Section 7.4 and 7.5  Event qualifies

Event	1st Action	2 nd A	Action	3rd A	Action	If event does not resolve
		If event does not resolve	If the event resolves	If event does not resolve	If the event resolves	 1650.776

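### The Section 6.3 trigger list makes an hour's persistence and a prior rate reduction conditions for entering Table 1, whereas Table 1 acts at the rating or sign itself

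*Combined protocol and SAP*

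**What the plan says.** Three places in Section 6.3 bear on when a side effect leads to a dose change.

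- **Trigger list** (Events that Trigger Dose Adjustment Procedures). The side-effect bullet opens "Persisting (i.e., unresolved within 1 hour of onset) side effects sedation, dizziness, lightheadedness", adds itchiness, bad dreams and hallucinations, and closes with "other side effects that are reported as not acceptable to patients or clinicians, despite minimizing infusion rate". The list then points to Table 1.
- **Patient-reported subsection** (Patient Reported Side Effects Dose Delays or Adjustments). A patient who rates an effect unacceptable "will follow the dose delay or adjustment described in the Table 1". If the effect is rated acceptable, "then no dose delays or adjustments will occur". No waiting time or earlier rate cut is mentioned.
- **Table 1.** The patient-rated row covers named effects and "other side effects rated by patient as Not Acceptable". Its first action is "Hold infusion for 10 minutes - symptom recheck every 10 min until resolution Supportive care medications in 9.1". A separate row covers RASS -2 or below or a respiratory rate under 8, and also starts with a 10-minute hold. In both rows, an hour without resolution leads to discontinuation at the investigator's discretion, and the rate is halved once the event resolves. Nausea or vomiting also has its own row, which starts with rescue medication and requires no acceptability rating.

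On timing, Section 1 states: "A loading dose over 1 hour will be the MTD variable to be tested, as our data suggest that ketamine side effects occur" with that load. Section 6.2 states: "The maintenance dose will start 60 min (range: +15min) after the initial loading dose".

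**The concern.** The heading of the trigger list tells staff when to open Table 1, but its conditions are not those of the table. The hour is an entry condition in one place and a stopping threshold in the other. Rate reduction is a precondition in one and a step of the procedure in the other. The list is also awkward read alone, since it asks for the rate to have been lowered before invoking the procedure that lowers it. No visible sentence says which text governs.

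This is a bedside safety rule in a trial that expects side effects during the hour of loading under test. Staff following the list to the letter could hold back when Table 1 calls for a hold. Two nurses following different paragraphs could also handle the same event differently.

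**Working it through.** The plan states no figure on this point, so the check is a comparison of the texts, followed by simple timing arithmetic.

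**Side by side**

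| Feature | Trigger list | Patient-reported subsection and Table 1 patient-rated row | Table 1 sedation/respiratory row |
|---|---|---|---|
| What opens the procedure | Effect still present an hour after it began, and unacceptable with the rate already lowered | The patient's unacceptable rating | RASS -2 or below, or respiratory rate under 8 |
| Role of one hour | Entry condition | Discontinuation threshold | Discontinuation threshold |
| Role of rate reduction | Precondition | Action after resolution | Action after resolution |
| Whose judgement | Patient or clinician | Patient | Clinical sign |

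**Does another parse remove the conflict?** Suppose the closing clause about acceptability and rate applies only to the unnamed other effects. The one-hour condition still covers the named effects and still disagrees with Table 1. A named effect that lasts over an hour but is rated acceptable would then trigger Table 1 under the list, while the subsection rules out any adjustment. The conflict moves but does not go away.

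**Sedation.** The trigger list names sedation, but the subsection's list of patient-reported effects does not. The subsection's mandatory instruction therefore does not rescue sedation. Only the Table 1 row contradicts the one-hour wait.

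**Upper bound on delay.** Inputs: one hour from onset (trigger list), a 60-minute load with up to 15 minutes' grace (Sections 1 and 6.2), and a 12-hour infusion (Section 6.2).

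- Wait allowed by the list's timing condition: 60 min from onset. Wait in Table 1: 0 min from the rating or sign.
- Share of the planned load period: 60/60 = 100%.
- Share if the load runs to its latest end: 60/(60 + 15) = 60/75 = 80%.
- Share of the whole infusion: 60/(12 × 60) = 60/720 = 8.3%.
- Wait remaining after a diary report: 60 − (report time − onset time), so never more than 60 min.

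These are ratios of clock time. They do not measure dose received or risk.

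**The case against.** The best defence is that the texts add to each other. The trigger list never says only, and nothing in it forbids acting sooner. The subsection is specific to patient-rated effects, is mandatory, and agrees with Table 1, so staff who act on the rating comply with everything. Other safeguards point the same way. Automated alerts call for immediate action (Sections 7 and 7.4), an anesthesia provider is present for the first 30 minutes (Section 7.4), patients are monitored throughout the infusion (Section 9.1), and the study team may change the rate at its discretion (Sections 6.2 and 7.3). The list may simply echo the persistence language of the DLT definition in Section 3.4.1. Figure 3, the decision chart, is not shown in the text available and may state the intended order.

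Much of this stands: for patient-rated effects, prompt action is the likely practice. It does not make the trigger list correct, and it does not cover sedation. The provider's required presence also ends before the 60-minute and later assessments.

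A reader might go further and infer that patients would receive the whole load untreated. Take an effect starting and rated at 15 minutes, resolving at the first 10-minute recheck, with the rate then halved. Table 1 gives 15/60 + 0.5 × 35/60 = 54% of the planned load, or 15/60 = 25% if the effect does not resolve within the loading hour. Setting 100% against these would ignore the list's own condition that the rate has already been lowered, as well as the team's discretion. The documents support no such dose contrast.

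**Conclusion.** The trigger list misstates when a side effect enters Table 1. The patient-reported subsection and Table 1 are probably the intended rule. The consequence is a possible delay of up to about one hour from onset, and only if staff apply the list literally. That bound takes the timing condition alone and assumes no earlier discretionary rate change or response to an alert.

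A reader might also infer that the DLT rule or the estimated maximum tolerated dose is affected. The documents do not support that: the DLT criterion in Section 3.4.1 and every stated figure are the same under either trigger. The point is worth correcting because it sits in a safety instruction, bears on consistent handling of the dose under test, and costs almost nothing to put right. Figure 3 could confirm the intended order, but the trigger list would still need rewording.

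**What to change.** In the Section 6.3 trigger list, leave the hemodynamic bullet alone. In the side-effect bullet, delete the one-hour persistence condition and the condition that the rate has already been minimized. State instead that the trigger is any event meeting a Table 1 row, namely:

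- a side effect the patient rates unacceptable, as the patient-reported subsection already provides;
- RASS -2 or below, or a respiratory rate under 8;
- nausea or vomiting, handled under its own row.

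Keep the one-hour criterion only at the discontinuation step in Table 1, and check that Figure 3 shows the same order.

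The trigger list also mentions effects that clinicians find unacceptable, for which the patient-rated row has no entry. This correction should not add a clinician-judged hold, halve and stop pathway while leaving DLTs patient-rated. A patient could then be discontinued for clinician-judged toxicity without counting as a DLT, and in a 3+3 design one uncounted event can change an escalation decision. Whether such effects should enter Table 1 and count as DLTs is a separate design decision for the sponsor.

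The cost is a rewording of one bullet and a check of one figure, with no change to the DLT criterion, sample size or analysis.
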